- Symptomatic Knee OA will be defined as the presence of a definite osteophyte or joint space narrowing (KL Grade ≥ 2) on posteroanterior (PA) fixed flexion knee radiographs in subjects limited by bilateral pain in each knee, rated on a Numerical Rating Scale as $\geq 4/10$ on more than half of the days over the past month. Radiographic change must be visible at standard image size, irrespective of capability to detect more subtle changes through digital enhancement.
- Bilateral knee symptoms for ≥ 3 months prior to screening.
- Undergone at least one prior conservative osteoarthritis treatment (e.g. physical therapy, analgesics).
- Body Mass Index ≤ 40 kg/m².
- Ambulatory.
- Willing and able to comply with the study procedures and visit schedules and ability to follow verbal and written instructions.
- Willing to abstain from the use of protocol-restricted medications during the study after signing Informed Consent (Refer to §II.5) and also willing to abstain from use of all analgesics other than acetaminophen 1 week prior to the beginning of treatment.

2. Exclusion Criteria

- Current consumption of more than 14 alcoholic drinks per week.
- Clinical signs and symptoms of active knee infection or crystal disease of either knee within 1 month of screening.
- Diagnosed with rheumatoid arthritis, Reiter's syndrome, psoriatic arthritis, gout, ankylosing spondylitis, or arthritis secondary to other inflammatory diseases; HIV, viral hepatitis; chondrocalcinosis, Paget's disease, or villonodular synovitis.
- Diagnosed with leukemia, known presence of metastatic malignant cells, or ongoing or planned chemotherapeutic treatment.
- Diseases of the spine, hip or other lower extremity joints judged by the investigator to be contributing to the pain in either knee (i.e. sciatica, nerve pain, hip OA). Note: Patients with hip replacement in either hip may be enrolled provided there is sufficient pain relief after hip replacement that analgesics are not required
- Untreated symptomatic injury of either knee (e.g., acute traumatic injury, anterior cruciate ligament injury, clinically symptomatic meniscus injury characterized by a mechanical issue such as locking or catching).
- Uncontrolled diabetes.

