- Aspirin for cardio-protection at a maximum stable dose provided the dose was stabilized over 3 months prior to study entry.
- Physical therapy/bracing for the knee joint if the program was initiated and consistent prior to study entry.
- Acetaminophen may be taken (up to 3000 mg per day) as rescue medication, if needed. Rescue medication is used only to treat worsening pain, whether or not that pain is associated with knee (e.g, may be used to treat headache, acute injury, etc.) and is not used for prophylaxis.
- Use of acetaminophen must be discontinued 48 hours prior to the procedure visit and each follow-up visit.

5. Restricted Medications/Nonpharmacological Therapies

Volunteers will be advised that participation in the study will require them to abstain from certain medications and therapies. The following medications and nonpharmacological therapies should not be taken or used beginning immediately upon enrollment (after signing informed consent) until subject reaches the end of the study:

- Oral non-steroidal anti-inflammatory drugs (unless on a chronic stable dose for ≥ 3 months prior to enrollment).
- Topical analgesics applied to the skin over the knee (e.g., NSAID's, capsaicin, lidocaine, heat patches).
- Orally administered systemic corticosteroids.
- Other Intra-articular injection into the knee joint.
- Centrally acting pain medications (e.g., pregabalin, gabapentin, duloxetine, milnacipran) (unless on a chronic stable dose for ≥ 3 months prior to enrollment).

E. Specific methods and techniques used throughout the study

Investigational Product

Zilretta kits will be received from Flexion Therapeutics and stored in a refrigerator between 2-8 degrees Celsius upon receipt. An 'Investigational Drug Accountability Record' will be used to record the product use for each subject. The kit label number, date of receipt, dates of dispense and preparation, and the date of destruction of the remaining product will be tracked and logged.

Treatment Procedure:

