A working group tasked with constructing a composite measure of OA severity sponsored by the Osteoarthritis Research Society International (OARSI) and Outcome Measures in Rheumatology (OMERACT) developed the KOOS-PS. Respondents are asked to indicate the degree of difficulty experienced in the last week due to a knee problem in 7 tasks: Rising from Bed, Putting on socks/stockings, Rising from sitting, Bending to the floor, Twisting/pivoting on the injured knee, Kneeling, and Squatting. Responses are measured on a Likert scale ranging from 'None' to 'Extreme'.

Tertiary Outcomes

KOOS QoL

KOOS-QoL is a self-reported measure¹³ (4 questions) of quality of life, which is part of the five patient-relevant subscales of KOOS. A Likert scale is used and all four questions have five possible answer options scored from 0 (No Problems) to 4 (Extreme Problems). Each of the five scores is calculated as the sum of the items included. Scores are transformed to a 0-100 scale, with zero representing extreme knee problems and 100 representing no knee problems as is common in orthopedic assessment scales and generic measures. Scores between 0 and 100 represent the percentage of total possible score achieved.

Numerical Rating Scale (NRS) for Pain

The Numeric Rating Scale for Pain (NRS for Pain) is a measure of pain intensity. The investigator or designee will verbally introduce the 11-point scale to the research subject to rate pain in each knee. The investigator or designee will ask the following questions,

- “On a scale of 0 to 10, with 0 being no pain at all and 10 being the worst pain imaginable, how would you rate your knee pain IN THE PAST 7 DAYS?”

The subject will complete the NRS for Pain worksheet after receiving instructions from the study coordinator. The NRS for Pain will be completed by the subject at baseline evaluation and at each follow-up visit (6,12 and 24 weeks). The study coordinator or designee will enter the data into the CRF.

The table below details the schedule of study assessments and procedures, for each visit.

Assessment	Visit 1 Screening	Visit 2 Day 1- Zilretta Treatment [‡]	Visit 3 6-Week Follow-up	Visit 4 12-Week Follow-up	Visit 5 24-Week Follow-up
Informed Consent	X				
Eligibility	X	X [‡]			
Medical history	X	X [‡]			
Radiograph (if not previously done)	X				
Concomitant medications	X	X [‡]	X	X	X
Prior/Concurrent Therapy	X				
Study Treatment		X			
BMI Assessment	X				
Physical Exam		X	X	X	X
KOOS-PS & QoL Questionnaire		X	X	X	X

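### The 1-week analgesic stop before treatment and the chronic stable-dose exemption are not aligned, so some subjects may be measured off drug at baseline and on drug at follow-up

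*Combined protocol and SAP*

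**What the plan says.** Three rules in section II.D govern analgesics.

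- **II.D.1 (Inclusion Criteria).** The last criterion asks for willingness to avoid the restricted medications after consent. It then adds a separate duty: subjects must be "also willing to abstain from use of all analgesics other than acetaminophen 1 week prior to the beginning of treatment". Chronic users get no exception.
- **II.D.5 (Restricted Medications).** The restrictions run "beginning immediately upon enrollment (after signing informed consent) until subject reaches the end of the study". Two entries carry an exemption: "Oral non-steroidal anti-inflammatory drugs (unless on a chronic stable dose for" at least 3 months before enrollment), and "Centrally acting pain medications (e.g., pregabalin, gabapentin, duloxetine, milnacipran) (unless on a chronic stable dose for" the same period). Nothing asks exempt users to stop before a follow-up visit.
- **II.D.4 (Allowable Medications).** Acetaminophen is handled alike at all visits: "Use of acetaminophen must be discontinued 48 hours prior to the procedure visit and each follow-up visit".

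In V.A the primary test is a paired t-test of the change from baseline to week 12. The secondary and tertiary models contain a subject effect and a time effect. Concomitant medications are scheduled at every visit, but V.A gives them no role in the analysis.

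**The concern.** Every subject receives Zilretta, so the estimated effect is simply the change from baseline. Anything else that differs systematically between baseline and follow-up is counted in it. A planned drug stop before baseline, with no matching stop before follow-up, is such a difference. A chronic user who stops for the week before treatment and then resumes would be expected to improve for a reason unrelated to the injection. No concurrent group would show the same improvement, and no model term would remove it. What is at stake is the size of the reported benefit, mainly in patient-reported function.

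**Working it through.** **Step 1. The rules side by side.**

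| Drug group | Week before treatment | Before weeks 6, 12 and 24 |
|---|---|---|
| Acetaminophen | Off for 48 hours | Off for 48 hours |
| Oral NSAID, chronic stable dose | Off for 1 week under II.D.1; may continue if II.D.5 is taken to prevail | May continue |
| Centrally acting drug, chronic stable dose | Same, provided these drugs count as analgesics in II.D.1 | May continue |
| Either class, not chronic stable dose | Off for 1 week under II.D.1; barred from consent | Barred |

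Only the two middle rows can differ between baseline and follow-up. II.D.1 joins its two duties as additional to each other, and the exemption qualifies only the restricted list. The cumulative reading is therefore natural, though not the only one.

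**Step 2. Which outcomes have a baseline inside the stop.**

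- *KOOS-PS.* Its first assessment is at Visit 2, the treatment visit. "Respondents are asked to indicate the degree of difficulty experienced in the last week due to a knee problem": that recall week coincides with the week of the stop. This is the clearest exposure.
- *KOOS-QoL.* Also first taken at Visit 2, but the protocol gives no recall period for it.
- *NRS pain.* The question is "how would you rate your knee pain IN THE PAST 7 DAYS". It is scheduled at both Visit 1 and Visit 2, and the text says only that "The NRS for Pain will be completed by the subject at baseline evaluation and at each follow-up visit". A Visit 1 score taken before the stop is not affected; a Visit 2 score is.
- *Performance tests (primary).* The schedule marks them at Visits 3 to 5 only. IV.A and V.A require a baseline without fixing its date. They are affected only if that baseline follows the stop.

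The schedule also allows treatment to be combined with screening. For a current user treated that day, no week of abstention can follow consent.

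**Step 3. Size, by illustration only.** The documents give neither the share of chronic users nor the effect of stopping, so both inputs below are assumptions.

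- Formula: shift in mean change = share off at baseline and on at follow-up × on/off difference, in SDs of change.
- Low: 0.10 × 0.1 = 0.01 SD. Middle: 0.20 × 0.2 = 0.04 SD. High: 0.50 × 0.4 = 0.20 SD.
- Scale: II.C plans for 60 evaluable subjects out of 70 (70 × 0.86 = 60.2, which agrees with the stated 14% dropout). The standard error of a mean change is 1/√60 = 0.129 SD.
- Shift in standard errors: 0.01/0.129 = 0.08; 0.04/0.129 = 0.31; 0.20/0.129 = 1.55.
- Share needed to move the estimate by half a standard error (0.0645 SD): 0.0645/0.1 = 65%; 0.0645/0.2 = 32%; 0.0645/0.4 = 16%.

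The shift is zero if chronic users continue unchanged through baseline. The high figure needs both assumed inputs at their maximum.

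**The case against.** The strongest reply is that no washout is actually imposed. II.D.1 is a willingness criterion, and no 1-week stop appears in II.D.4, II.D.5 or the schedule. The II.D.5 exemption runs from consent, so it covers the pre-treatment period. Staff who applied it there would keep chronic users on drug throughout. This stands: a reader might infer that every chronic user is taken off drug before baseline, and the text does not establish that. It does not remove the point, because an eligibility condition covering all analgesics except acetaminophen can just as reasonably be applied as written, and staff could apply it differently from one subject to the next.

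A second reply is that II.D.1 does not say whether analgesics include drugs such as gabapentin or duloxetine. This also stands. NSAIDs are certainly covered; centrally acting pain drugs probably are.

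A third reply is that existing controls limit the problem. New NSAIDs, topical analgesics over the knee and new centrally acting drugs are barred to study end, medications are recorded at every visit, and noncompliant subjects may be discontinued. A raised dose could fairly be said to fall outside a stable-dose exemption, although the stability condition looks only at the period before enrollment. These controls limit drift after treatment. They do not address a permitted return to the usual dose.

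A reader might also infer that the primary result is biased or its type I error inflated. The documents do not support that: the date of the performance baseline is not given, and any error rate would rest entirely on assumed inputs.

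**Conclusion.** The point holds as a misalignment between two rules, not as a flat contradiction and not as a demonstrated bias. Under the cumulative reading, chronic stable-dose users may be off drug before treatment and on drug at each follow-up, and the single-arm analysis would credit the difference to Zilretta. If the exemption is applied before treatment, the asymmetry disappears. KOOS-PS is the outcome most clearly exposed; NRS pain and the primary tests are exposed only if their baseline follows the stop.

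The size cannot be derived from the documents. Over the assumed ranges it runs from 0.01 to 0.20 SD of change, and it is small unless chronic use is common or the effect of stopping is large. The change is still worth making: the trial has no other protection against this difference, and the correction is cheap.

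**What to change.** Amend II.D.1 and II.D.5 together:

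- Exempt subjects on a chronic stable dose of an oral NSAID or a centrally acting pain drug from the 1-week stop.
- Require them to keep that dose constant from consent to week 24.

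The same rule then applies to these subjects at baseline and at every follow-up visit, whichever visit supplies the NRS or performance baseline. From the concomitant-medication records already scheduled, report how many subjects' analgesic status differed between baseline and week 12.

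The cost is a short amendment and one descriptive count. No new data are collected and the planned sample size does not change. The drawback is that chronic users' baseline is measured on drug, which may leave them less room to improve.

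### The 1-week analgesic stop before treatment has no stable-dose exemption, so a stable NSAID or centrally acting drug user may be off drug at a Day 1 baseline and, if they resume as allowed, on drug at follow-up

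*Combined protocol and SAP*

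**What the plan says.** One inclusion bullet in II.D.1 carries two duties. It opens with "Willing to abstain from the use of protocol-restricted medications during the study after signing Informed Consent (Refer to §II.5" and then adds that the subject is "also willing to abstain from use of all analgesics other than acetaminophen 1 week prior to the beginning of treatment". The first duty points to the restricted list. The second stands alone: it covers all analgesics, names acetaminophen as the only exception, and is tied only to the start of treatment.

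The restricted list in II.D.5 applies "beginning immediately upon enrollment (after signing informed consent) until subject reaches the end of the study". Two of its entries carry an exemption:

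- "Oral non-steroidal anti-inflammatory drugs (unless on a chronic stable dose for ≥ 3 months prior to enrollment"
- "Centrally acting pain medications (e.g., pregabalin, gabapentin, duloxetine, milnacipran) (unless on a chronic stable dose for ≥ 3 months prior to enrollment"

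Nothing in II.D.5 asks exempt users to stop before the 6-, 12- or 24-week visits. Acetaminophen is handled differently in II.D.4: "Use of acetaminophen must be discontinued 48 hours prior to the procedure visit and each follow-up visit".

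Two outcomes in II.E look back over a week. KOOS-PS asks for the "degree of difficulty experienced in the last week due to a knee problem", and the pain NRS asks "how would you rate your knee pain IN THE PAST 7 DAYS".

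Under V.A, the primary analysis is a paired t-test on 12-week change in each of the three performance tests. The models for the other outcomes contain only a subject effect and a time effect. All subjects are treated (II.C).

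**The concern.** In a single-arm before/after study the baseline is the only comparator, so analgesic conditions at baseline and follow-up have to match. The acetaminophen rule achieves this by naming the procedure visit and the follow-up visits together. The 1-week rule, which governs the other analgesics, does not.

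A long-term NSAID user who stops for the week, is assessed on Day 1 and then restarts the usual drug breaks no rule. Part of that person's improvement would come from restarting, and the analysis has no means of separating it from the effect of the injection. Stopping a useful analgesic would be expected to worsen baseline pain and function, so the error would probably make the product look better.

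**Working it through.** **Step 1. The rules side by side, as written.**

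| Drug | Week before Day 1 | Before 6-, 12- and 24-week visits | Matched? |
|---|---|---|---|
| Acetaminophen | Allowed until 48 h before | Allowed until 48 h before | Yes |
| Oral NSAID, not stable | Stopped | Not allowed | Yes |
| Oral NSAID, chronic stable | Stopped | Allowed, no stop | No, if resumed |
| Centrally acting, not stable | Stopped | Not allowed | Yes |
| Centrally acting, chronic stable | Stopped | Allowed, no stop | No, if resumed |

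The last two rows assume that the centrally acting drugs count as analgesics. II.D.5 itself calls them pain medications, so this is reasonable, but the 1-week rule does not name them.

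**Step 2. Which outcomes are reached.**

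- KOOS-PS: the only pre-treatment mark in the schedule is Visit 2 (Day 1). Its one-week recall is then the stop week.
- NRS pain: marked at screening and at Visit 2. If the Visit 2 value is the baseline, its 7-day recall is also the stop week.
- Performance tests: the schedule as extracted marks only Visits 3 to 5, although IV.A says that they are collected at baseline. If that baseline is on Day 1, they are exposed. If it precedes the stop, they are not.

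**Step 3. Effect on the estimate.** Let f be the share of analysed subjects who are stable users, stop for the week and later resume. Let g be their on-drug minus off-drug difference, in SDs of change. The expected mean change is then the true change plus f × g. Neither f nor g is in the documents.

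**Step 4. The plan's own yardstick.** II.C gives effect size 0.392, alpha 0.0167, power 80% and N = 60, recruiting 70 for 14% dropout. A paired t-test (noncentral t) with these inputs needs n = 60 one-sided (power 80.2%), which reproduces the figure. Two-sided it needs 71 (power 71.5% at 60). Dropout: 60 / (1 − 0.14) = 69.8, so 70. The plan does not state sidedness. That is a separate matter, so both versions are shown below.

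**Step 5. Illustration under assumed f and g.** Take 0.392 as SDs of change, n = 60 and no true drug effect. The chance of a significant benefit on one exposed test is P(T > critical value), where T is noncentral t with 59 df and noncentrality √60 × f·g / √(1 + f(1 − f)g²).

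| f (assumed) | g (assumed) | Shift f × g | Share of 0.392 | One-sided 0.0167 | Two-sided 0.0167, benefit side |
|---|---|---|---|---|---|
| 0.1 | 0.2 | 0.02 | 5% | 2.4% | 1.2% |
| 0.2 | 0.3 | 0.06 | 15% | 4.7% | 2.6% |
| 0.3 | 0.5 | 0.15 | 38% | 15.5% | 9.9% |
| 0.5 | 0.5 | 0.25 | 64% | 38.8% | 28.8% |

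The nominal rates are 1.67% and 0.83%.

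**Step 6. Bound.** For the mismatch alone to produce a shift of 0.392, g would have to be 0.392 / f: 3.92 SD at f = 10%, 1.57 SD at 25% and 0.98 SD at 40% (assumed shares).

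**The case against.** The strongest case is that this is an ambiguity in drafting and not a demonstrated bias.

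- **Resumption is permitted, not required.** A reader might infer that every stable user who follows both rules is off drug at baseline and on drug at 12 weeks. The text does not say that: a user who stops and stays off also complies. This stands, and it is why the point is conditional.
- **A matched reading exists.** The II.D.5 restriction and its exemption start at consent. Where consent comes a week or more before Day 1, they cover the same week as the stop. A site that lets the specific exemption override the general stop keeps stable users on drug throughout, with no mismatch. This also stands, but nothing in the documents says which clause prevails, and staff could apply the rule differently to different subjects.
- **Reach to the primary outcome is assumed.** A reader might infer that the primary result is biased. The documents do not fix the visit for the baseline performance tests, and the schedule table may have been damaged in extraction, so the inference is not supported.
- **There are mitigations.** Concomitant medications are marked at all five visits, so stops and restarts need not go unrecorded, although time of last dose may not be captured and V.A makes no use of the record. Acetaminophen is allowed on about 5 of the 7 recall days (7 days less 48 hours), which could soften the off-drug week.

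A reader might also infer that combining screening with treatment waives the stop. The schedule footnote does not say so, and the telephone pre-screen may announce the rule in advance.

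**Conclusion.** The point holds in conditional form. The two rules as written permit an off-drug Day 1 baseline against an on-drug follow-up for chronic stable users of oral NSAIDs and centrally acting pain drugs, and no other part of the protocol reconciles them. KOOS-PS is the clearest case, NRS pain follows if its baseline is the Day 1 value, and the performance tests follow only if their baseline is taken then too. The likely direction favours the product, and the single-arm, unadjusted analysis cannot remove it.

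The size cannot be determined from the documents. It may be zero, if no stable users enrol, if they do not resume, or if sites apply the exemption to the stop week. The illustrations above rest on assumed values and show only that modest shifts can matter at n = 60. A reader might infer that the mismatch could account for the whole planned effect. The bound makes that implausible at low shares of stable users, so the realistic worry is an inflated estimate. The change is worth making because it is nearly free; confidence is medium.

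**What to change.** Apply one rule to baseline and to every follow-up.

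- Preferred: add the chronic stable-dose exemption of II.D.5 to the 1-week clause in II.D.1, so that these drugs continue unchanged throughout.
- Alternative: withhold them for the same period before Day 1 and before each follow-up assessment, as is already done for acetaminophen.
- In either case, use the concomitant medication record already taken at each visit to confirm that conditions at baseline and follow-up matched.

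The cost is a few words in one eligibility bullet. Under the preferred version, stable users are assessed at baseline on their usual drug, so their baseline reflects treated symptoms. The sample size stays at 60 evaluable and 70 recruited. The alternative asks stable users to go without their drug before every assessment visit.
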